2. The trial will be conducted in accordance with International Council on Harmonisation Good Clinical Practice (ICH GCP), applicable United States (US) Code of Federal Regulations (CFR), and the [specify NIH Institute or Center (IC)] Terms and Conditions of Award. The Principal Investigator will assure that no deviation from, or changes to the protocol will take place without prior agreement from the funding agency and documented approval from the Institutional Review Board (IRB), and the Investigational New Drug (IND) or Investigational Device Exemption (IDE) sponsor, if applicable, except where necessary to eliminate an immediate hazard(s) to the trial participants. All personnel involved in the conduct of this study have completed Human Subjects Protection and ICH GCP Training.

For either option above, the following paragraph would be included:

The protocol, informed consent form(s), recruitment materials, and all participant materials will be submitted to the IRB for review and approval. Approval of both the protocol and the consent form(s) must be obtained before any participant is consented. Any amendment to the protocol will require review and approval by the IRB before the changes are implemented to the study. All changes to the consent form(s) will be IRB approved; a determination will be made regarding whether a new consent needs to be obtained from participants who provided consent, using a previously approved consent form.

1 PROTOCOL SUMMARY

1.1 SYNOPSIS

Title:	Duramorph Study Design: Prospective, Randomized Double Blinded
Study Description:	Prospective double blind randomized control trial
Objectives:	Primary Objective: Analyze impact of epidural morphine on pain management for vaginal delivery VD Secondary Objectives: Analyze impact of epidural morphine on recovery and depression
Endpoints:	Primary Endpoint: Opiate consumption at 24 hours Secondary Endpoints: Pain score at 24 hours, obstetric recovery score at 24 hours, Edinburgh post partum depression scale at 6 weeks, breast feeding success at 1 week
Study Population:	Pregnant women over 18
Phase:	4
Description of Sites/Facilities Enrolling Participants:	KP2 Labor floor at Mount Sinai Hospital
Description of Study Intervention:	Epidural morphine 2mg vs placebo
Study Duration:	4 years
Participant Duration:	6 weeks

1.2 SCHEMA

1. Obtain consent
2. 1 hour delivery administer study drug or placebo
3. 24 hours after collect data on opiate administration, pain score, and recovery score
4. 1 week after administration call patient inquire about breast feeding
5. At 6 weeks after administration call patient and administer post partum depression screen

1.3 SCHEDULE OF ACTIVITIES (SOA)

1. Obtain consent
2. 1 hour delivery administer study drug or placebo
3. 24 hours after collect data on opiate administration, pain score, and recovery score
4. 1 week after administration call patient inquire about breast feeding
5. At 6 weeks after administration call patient and administer post partum depression screen

2 INTRODUCTION

2.1 STUDY RATIONALE

There is no current standard of care for post vaginal delivery pain. Many different options exist, however, their impact on minimizing opiate utilization have been minimal. As such, we are investigating the utility of a single dose of preservative free morphine on pain scores in the post partum period.

2.2 BACKGROUND

There is no gold standard for pain management in NSVD. There is some evidence that preservative free morphine is effective at pain relief for cesarean deliveries. The relationship between pain and epidural morphine for NSVD has not been investigated.

2.3 RISK/BENEFIT ASSESSMENT

2.3.1 KNOWN POTENTIAL RISKS

Risks can include nausea, vomiting, itching, respiratory depression

2.3.3 ASSESSMENT OF POTENTIAL RISKS AND BENEFITS

Benefits include less oral and IV opiate use which also cause nausea, itching and respiratory depression. Benefits may also include a faster recovery and more breast feeding. The risks of this dose of morphine are small and have been used for cesarean delivery for decades.

3 OBJECTIVES AND ENDPOINTS

OBJECTIVES	ENDPOINTS	JUSTIFICATION FOR ENDPOINTS
Primary		
	Opiate consumption at 24 hours	Opiate use should be minimized due to side effects
Secondary		
	Pain score at 24 hours Recovery score at 24 hours Breast feeding rate at 1 week Post partum depression screen at 6 weeks	Better pain control is good endpoint, as is recovery. Breastfeeding can have long term impacts on both mom and baby and it's impact should be investigated. Depression is a major issue post partum and controlling pain in the immediate post partum period may help with that.
Tertiary/Exploratory		

4 STUDY DESIGN

4.1 OVERALL DESIGN

Double blind, prospective, randomized control trial

4.2 SCIENTIFIC RATIONALE FOR STUDY DESIGN

When investigating the impact of a medication on pain, opiate consumption, etc, it is important for the study to be blinded and randomized to avoid bias.

4.3 JUSTIFICATION FOR DOSE

This dose is commonly administered to pregnant women for cesarean delivery. It has an excellent safety profile and a long history of use.

4.4 END OF STUDY DEFINITION

Patients complete their involvement after their 6 weeks post partum depression screen

5 STUDY POPULATION

5.1 INCLUSION CRITERIA

18 years old, pregnant, presenting for VD

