5.2 EXCLUSION CRITERIA

Refusal of neuraxial anesthesia, allergy to morphine, patients with chronic pain syndromes or chronic opiate use.

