6.1.2 DOSING AND ADMINISTRATION

2 mg (4ml) will be administered one hour after the patient has their VD. It will be administered through their in situ epidural

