9.4.2 ANALYSIS OF THE PRIMARY EFFICACY ENDPOINT(S)

Wilcoxon rank sum

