9.4.5 BASELINE DESCRIPTIVE STATISTICS

Given randomization we will simply report, not analyze

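### The pooled rank-sum test is valid for all vaginal deliveries, but it ignores delivery type, which is fixed before dosing, and no NSVD-specific result is pre-specified

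*Combined protocol and SAP*

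**What the plan says.** **Population.** Inclusion (5.1) is "18 years old, pregnant, presenting for VD". The exclusions (5.2) are "Refusal of neuraxial anesthesia, allergy to morphine, patients with chronic pain syndromes or chronic opiate use"; none concerns how the birth went. Section 6.3 repeats that every VD patient is eligible. The rationale (2.1) opens with "There is no current standard of care for post vaginal delivery pain", and the primary objective in the synopsis (1.1) is "Analyze impact of epidural morphine on pain management for vaginal delivery VD". The background (2.2) is narrower: "The relationship between pain and epidural morphine for NSVD has not been investigated". NSVD is not in the abbreviation list (10.3); I read it as normal spontaneous vaginal delivery.

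**Timing.** Section 6.1.2 says "2 mg (4ml) will be administered one hour after the patient has their VD". Section 5.4 implies, without saying so outright, that randomization also follows delivery.

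**Analysis.** The whole of 9.4.2 is "Wilcoxon rank sum". Section 6.3 names no stratification factor, and 9.4.7 marks subgroups as not applicable. On baseline data, 9.4.5 says "Given randomization we will simply report, not analyze" and lists no variables. Delivery mode and tear grade are not named as data items anywhere.

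**The concern.** With no exclusion on the delivery itself, instrumental births and severe perineal tears can be enrolled alongside uncomplicated spontaneous births. The documents never mention them; their inclusion follows from the absence of a restriction. If these women need much more opiate in the first 24 hours, three things follow:

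- Variation between delivery types goes into the noise of the primary test, although a stratified test could remove it.
- A chance imbalance in complicated births between arms shifts the estimate.
- The pooled result may be driven largely by the complicated minority, and a reader interested in the group named in 2.2 would find no planned result for it. Because delivery type is not a listed data item, even a later breakdown is not assured.

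**Working it through.** **1. The plan's own figure.** Section 9.2 gives 60 per group for a 25% reduction, raised to 150 per group. It states no alpha, sidedness, power, mean or SD, so the 60 cannot be reproduced. Assuming two-sided alpha 0.05, 80% power and a comparison of means, I solve for the coefficient of variation (CV, SD/mean) that yields 60:

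CV = 0.25 / [√(2/60) × (1.960 + 0.842)] = 0.25 / 0.511 = 0.489.

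Other choices of sidedness (one or two), power (80% or 90%) and allowance for rank-test efficiency give 0.41 to 0.55.

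**2. Continuous-outcome illustration (all inputs assumed).** Let spontaneous births have mean 1, and complicated births have share q and mean r. Take CV c = 0.489 within each type and a 25% reduction in both.

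- Overall mean m = 1 − q + qr
- Within-type variance = (1 − q)c² + q(cr)²
- Between-type variance = q(1 − q)(r − 1)²
- n per group = 2 × (1.960 + 0.842)² × (CV/0.25)²

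Example with q = 20%, r = 2: m = 1.2, within 0.382, between 0.160. Unstratified CV = √0.542/1.2 = 0.614, so n = 95. Stratified CV = √0.382/1.2 = 0.515, so n = 67.

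| q, r | n per group, unstratified | n per group, stratified | Power at 150, unstratified | Power at 150, stratified |
|---|---|---|---|---|
| 10%, 1.5 | 67 | 62 | 98.8% | 99.2% |
| 20%, 2 | 95 | 67 | 94.2% | 98.8% |
| 30%, 3 | 163 | 80 | 76.9% | 97.0% |

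**3. Simulation of the actual test.** The model in step 2 inherits its CV from the unverified 60 and has no non-users. Opiate use after vaginal birth may include many zeros, so I also compared the plain tie-corrected rank sum with van Elteren's test. The latter sums (W_k − E[W_k])/(N_k + 1) over strata and divides by the square root of Σ Var(W_k)/(N_k + 1)².

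Settings: 150 per arm, two-sided 5%, 2,500 replicates (simulation error about 1 point), lognormal amounts among users (log-scale SD 0.6), with treatment reducing the share of users. All use rates are assumptions. Power is shown as plain, then stratified.

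| Complicated share; users in complicated vs other births | 25% reduction | 50% reduction |
|---|---|---|
| 10%; 50% vs 20% | 24%, 24% | 76%, 75% |
| 15%; 50% vs 25% | 31%, 31% | 85%, 86% |
| 20%; 50% vs 30% | 35%, 35% | 92%, 92% |
| 10%; 60% vs 15% | 20%, 20% | 67%, 69% |
| 15%; 70% vs 15% | 24%, 26% | 75%, 80% |
| 25%; 80% vs 10% | 28%, 36% | 85%, 92% |
| 30%; 90% vs 10% | 35%, 47% | 92%, 97% |

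Type I error was 4% to 6% for both tests.

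**4. Who drives the pooled result.** In the 25%; 80% vs 10% case, expected placebo-arm users are 0.25 × 0.80 = 0.20 from complicated births and 0.75 × 0.10 = 0.075 from the rest. Complicated births supply 0.20/0.275 = 73% of users.

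**5. Chance imbalance.** For a 20% stratum at 150 per arm, the SD of the between-arm difference in its share is √(2 × 0.2 × 0.8/150) = 4.6 percentage points.

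**The case against.** A reader might infer that the trial's rationale is NSVD, that eligibility contradicts it, and that the trial cannot answer for NSVD. The documents do not support this. The rationale section and the primary objective speak of vaginal delivery, as do eligibility and dosing; NSVD appears only in the background. Randomization keeps the plain test valid for VD, as the type I error confirms. An NSVD subset could be analysed if delivery type were recorded.

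The other objections, and what stands of each:

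- **No passage says opiate need differs by delivery type.** This stands. The contrast is an assumption, and with mild contrasts the simulated gain is nil or within simulation error.
- **Recruiting 150 against a stated need of 60 absorbs the noise.** This stands in part. In step 2, unstratified power stays at or above 93% for q up to 30% and r up to 2. But that reassurance uses a CV solved from the same unverified 60, and it weakens if many women take no opiate.
- **Power for the plan's own 25% reduction is low in every simulated case, and stratification does not rescue it.** This stands: 20% to 35% for the plain test, at most 47% stratified. It is a separate sample-size matter.
- **Reporting baseline data without testing it, and enrolling broadly, are accepted choices.** This stands. Section 9.4.5 is not an error and does not forbid listing delivery type or using it in the analysis.

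**Conclusion.** The point holds as a cheap improvement in efficiency and clarity; it does not correct an invalid analysis. The documents establish that eligibility is any VD, that the primary test is unstratified, that no subgroup result is planned, that delivery type is not a named data item, and that 2.2 uses a narrower term than the rest. The birth precedes dosing by an hour, so the study drug cannot affect delivery mode or tear, and stratifying on them is legitimate.

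At 150 per arm the gain in power is about:

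- 0 to 2 points with 10% to 20% complicated births and 50% to 60% vs 15% to 30% using opiates;
- 2 to 5 points with 15% complicated and 70% vs 15%;
- 5 to 12 points with 25% to 30% complicated and 80% to 90% vs 10%.

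These figures rest on assumed use rates, an assumed amount distribution and an effect acting on the share of users. Which case applies cannot be told from the documents. The supportable statement on NSVD is that no result for it is pre-specified and the item needed to produce one is not planned.

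**What to change.** 1. Before dosing, record from the delivery note one two-level factor: spontaneous delivery without severe tear, or instrumental delivery or severe tear.
2. In 9.4.2, with a matching line in 9.4.1, make the primary test a rank-sum test stratified on that factor (van Elteren).
3. Report 24-hour opiate consumption by arm within each level, labelled descriptive, so that the result in spontaneous births is visible.
4. Define NSVD and reconcile 2.2 with 1.1, 2.1 and 5.1, stating whether the target population is all VD or NSVD.

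Stratifying the randomization list is optional; the stratified test works without it.

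The cost is one chart field, slightly more analysis work and a few lines of text. Sample size and treatment are untouched. The downside is little gain if few births are complicated.

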5.2 EXCLUSION CRITERIA

Refusal of neuraxial anesthesia, allergy to morphine, patients with chronic pain syndromes or chronic opiate use.

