7.3 LOST TO FOLLOW-UP

Given that one of our endpoints is 6 weeks out we expect to lose some patients to follow up. This will impact our findings, however, our study is powered for our primary endpoint which is opiate consumption at 24 hours. We expect little or no followup loss for this endpoint.

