9.4.3 ANALYSIS OF THE SECONDARY ENDPOINT(S)

Recovery score and depression score: Wilcoxon Rank Sum, Breast feeding: Chi square

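### No pre-dose depression status is specified, so the 6-week Edinburgh comparison loses precision and neither chance imbalance nor selective loss can be checked

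*Combined protocol and SAP*

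**What the plan says.** The synopsis (1.1) gives the secondary objective as "Analyze impact of epidural morphine on recovery and depression" and lists among the secondary endpoints the "Edinburgh post partum depression scale at 6 weeks". The schema (1.2) and schedule of activities (1.3) have one depression assessment, the 6-week telephone call. The only step listed before dosing is consent.

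Eligibility is "18 years old, pregnant, presenting for VD" (5.1), less the exclusions in 5.2: "Refusal of neuraxial anesthesia, allergy to morphine, patients with chronic pain syndromes or chronic opiate use". Neither section mentions depression or antidepressant treatment.

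For the analysis, 9.4.3 says "Recovery score and depression score: Wilcoxon Rank Sum", with no covariate or stratum; 9.1 names the same test. Section 9.3 calls for intention to treat among all randomized women. On baseline data, 9.4.5 says "Given randomization we will simply report, not analyze" and names no variables. On follow-up, 7.3 says "Given that one of our endpoints is 6 weeks out we expect to lose some patients to follow up". No method for missing 6-week scores is described.

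**The concern.** Some women will enter the trial with a history of depression or on treatment for it, and their 6-week scores are likely to be higher than those of other women. If that status is not recorded before dosing, four things follow.

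- The spread due to prior depression stays in the error term, so the comparison is less precise than it could be.
- A chance imbalance between arms can be neither described nor adjusted for.
- Loss by 6 weeks is expected. Randomization protects the full randomized set, not the subset reached by telephone. If loss depends on prior depression and does so differently by arm, the comparison among women reached is biased, and nothing specified would reveal it.
- Continuing depression cannot be told apart from new-onset depression when the 6-week scores are described.

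**Working it through.** **The plan's own figures.** No sample size, SD or target difference is given for depression. Section 9.2 concerns the primary endpoint: 60 per group, raised to 150. That step implies 1 − 60/150 = 60% loss. The 60 cannot be re-derived because no SD, alpha or power is stated, and it does not bear on this point. Below, 150 and 60 per arm serve only as outer limits for the number reached at 6 weeks. Every other input is an illustrative assumption.

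**1. Does unrecorded prior depression bias the randomized comparison?** The planned Wilcoxon test was simulated with 150 per arm, residual SD 4, prior depression adding 6 points, and 4,000 trials per setting.

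| Prevalence of prior depression | Rejection rate, no true effect | Power, true effect 1.5 points |
|---|---|---|
| 0% | 5.0% | 88% |
| 10% | 5.0% | 83% |
| 20% | 5.3% | 78% |
| 30% | 4.8% | 73% |

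With no true effect, the mean difference between arms lay between −0.02 and 0.01. There is no systematic bias and the type I error holds. The cost is power.

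**2. What would adjustment recover?** Normal approximation, two-sided 0.05: power = Φ(d√(n/2) − 1.96), with d = 1.5/5 = 0.30 unadjusted.

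- Charted history, 20% of women, 4 points higher: R² = 0.2 × 0.8 × 4²/5² = 0.10, so d becomes 0.30/√0.90 = 0.316.
- Baseline Edinburgh score correlated 0.5 with the 6-week score: R² = 0.25, so d becomes 0.30/√0.75 = 0.346.

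| Reached per arm | Unadjusted | Charted history | Baseline score |
|---|---|---|---|
| 60 | 38% | 41% | 47% |
| 100 | 56% | 61% | 69% |
| 150 | 74% | 78% | 85% |

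For n = 100, √(100/2) = 7.071. The arguments of Φ are 2.121 − 1.96 = 0.161, 2.236 − 1.96 = 0.276 and 2.449 − 1.96 = 0.489. This is a formula for means, so it only approximates the power of rank tests.

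In terms of detectable difference (150 per arm, 80% power), √(2/150) × (1.96 + 0.842) = 0.323 SD unadjusted. Multiplying by √(1 − r²) gives 0.309, 0.280 and 0.231 SD for r = 0.3, 0.5 and 0.7.

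**3. How large could chance imbalance be?** The 95% range is ±1.96√(2p(1 − p)/n).

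| Per arm | p = 10% | p = 20% |
|---|---|---|
| 150 | ±6.8 points | ±9.1 points |
| 100 | ±8.3 points | ±11.1 points |
| 60 | ±10.7 points | ±14.3 points |

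**4. How large could bias from selective loss be?** Suppose 20% have prior depression and score 4 points higher. Suppose 70% of them are reached in one arm and 50% in the other, against 67% of other women in both. The share with prior depression among those reached is 0.140/(0.140 + 0.536) = 20.7% in one arm and 0.100/(0.100 + 0.536) = 15.7% in the other. The bias is (0.207 − 0.157) × 4 ≈ 0.2 points. That is small beside a difference of 1.5, but under the plan as written the investigators could not show that it is small.

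**The case against.** A reader might infer that the 6-week comparison mixes prior depression with the treatment effect, or that 5.2 is at fault for admitting women who are already depressed. The documents do not support this. The trial is randomized, double blind and placebo controlled with intention-to-treat analysis, so prior depression is balanced in expectation, and step 1 shows the test keeping its error rate. An unadjusted rank-sum test is valid here.

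Nor do the documents show that 5.2 was written to protect the opiate endpoint while depression was forgotten. The only reason given for excluding women on opiates, in 6.5.1, concerns synergy with the study drug. It would also be too much to say that depression status will not be recorded: 9.4.5 leaves the baseline variables open, so the accurate statement is that none is specified.

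Three further objections have weight. Bias from loss needs loss that is related to prior depression and differs by arm after a single blinded dose, and nothing in 7.3 points to either. The principal investigator keeps a linking code (10.1.3), so chart history could in principle be abstracted later, subject to approval. And this is a secondary endpoint; 7.3 says the trial is powered for the primary one.

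These points limit the concern to a modest one but do not remove it. The loss of precision and the inability to check balance or follow-up remain. A stratum chosen after the data are seen lacks the standing of a prespecified one, and a pre-dose Edinburgh score cannot be obtained after dosing.

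**Conclusion.** The concern holds as a gap in precision and in what can be checked, not as confounding and not as an error in eligibility. With the stated assumptions and 100 women per arm at 6 weeks, charted history raises power by about 5 percentage points (56% to 61%) and an optional baseline score by about 12 to 13 (56% to 69%). Over 60 to 150 per arm, the gain from charted history is roughly 3 to 5 points. The SD, the difference, the prevalence, the score shift and the correlation are all assumed, and the gain shrinks if prior depression predicts the 6-week score less well. Bias from selective loss is possible but speculative, about 0.2 points in the example. This is an inexpensive improvement to a secondary analysis and does not threaten the validity of the trial.

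**What to change.** Leave 5.1 and 5.2 as they are.

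- Before randomization, record from the chart any history of depression or current antidepressant use, as one yes/no field. Name it in 9.4.5 as a baseline variable reported by arm.
- In 9.4.3, compare 6-week Edinburgh scores with a rank-sum test stratified on that field (van Elteren). This keeps the rank-based approach of 9.4.1.
- Report the number reached at 6 weeks by arm within each stratum.
- Optional, if acceptable to participants: give the Edinburgh scale at consent and use it as the covariate in a rank-based ANCOVA.

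The cost is one chart field, a sentence or two in 9.4.3 and 9.4.5, and slightly more analysis work. The optional questionnaire adds a few minutes at consent. The stratified test deals with loss only so far as loss depends on the recorded factor. It does not replace a stated method for missing 6-week scores.

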5.3 LIFESTYLE CONSIDERATIONS

Not applicable for this study.

5.4 SCREEN FAILURES

Patients are consented when they have adequate pain control and are in labor. Due to patient convenience patients may consent to participate but not be randomized based on their time of delivery. These patients will be kept in a separate log.

5.5 STRATEGIES FOR RECRUITMENT AND RETENTION

We will use the clinical anesthesia team to inform us of potential patients. They have been educated about the study.

6 STUDY INTERVENTION

6.1 STUDY INTERVENTION(S) ADMINISTRATION

6.1.1 STUDY INTERVENTION DESCRIPTION

Epidural morphine 2mg

6.1.2 DOSING AND ADMINISTRATION

2 mg (4ml) will be administered one hour after the patient has their VD. It will be administered through their in situ epidural

